#### 11 STATISTICAL CONSIDERATIONS

#### 11.1 Study Hypotheses.

For this study, we hypothesize:

- Dental health care workers will be willing to participate
- Surveys will be easy to complete
- Testing protocols will be easy to complete

Analyses will be performed to test these hypotheses.

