## **3 OBJECTIVES AND OUTCOME MEASURES**

## 3.0 Rutgers DHCW Feasibility Study Outcomes

PILOT Objectives	Brief Description/Justification of Outcome Measure	Outcome Measured By	Time Frame
To Determine DHCW Willingness to Participate	Willingness to participate is important in determining whether dental offices, DHCW would be willing to participate in a large-scale study	
 
Ratio of DHCW agreeing to participate as compared to all DHCW asked to participate
 
Thoroughness of consent process and ability to ask questions
 
	
 
Willingness to Participate:
 
DHCW – at time of consent by DHCW consent
 

To Determine DHCW and Willingness/Ability to follow through with Triage, Testing and Survey Administration Procedures	Determining willingness and ability to follow thru with triage, testing and survey administration procedures is important for refining the survey procedures	
 
% who complete the study
 
% who complete surveys         
 
Start-of-Study DHCW Survey
 
End-Of-Study DHCW Survey
 
 
 
% who feel testing (Saliva, PCR, POC, and ELISA Antibody) procedure was easy to comply with         
 
Specimen collection
 
Specimen preparation for shipping
 
Specimen storage (till assay)
 
Timeliness of results
 
Reporting of results
 
 
 
	
 
% Complete Study:
 
For DHCW - At time End-of-Study (Day 28)
 
% All Surveys Completed:
 
For DHCW - At time End-of-Study (Day 28)
 
% Feel Testing Protocol was Easy to Comply With:
 
For DHCW - At time End-of-Study (Day 28)
 

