To Determine Ease of Use with REDCap Survey Instruments • Dental Health Care Worker Subject • Start-of-Study Survey • End-of-Study Survey • Triage Survey	Determining the ease of use and completeness of the REDCap instruments enables refinement of the system	
 
% who feel surveys are easy to complete due to administration method:         
 
Start-of-Study DHCW Survey
 
End-of-Study DHCW Survey
 
Triage Case Report
 
 
 
% who feel survey questions were understandable:         
 
Start-of-Study DHCW Survey
 
End-of-Study DHCW Survey
 
Triage Case Report
 
 
 
% completed surveys:         
 
Start-of-Study DHCW Survey
 
Triage Case Report
 
 
 
% completed surveys:         
 
Start-of-Study DHCW Survey
 
Triage Case Report
 
 
 
	
 
% indicating surveys were easy to complete due to administration method:
 
For DHCW - At time End-of- Study (Day 28)
 
% indicating survey questions were easy to understand:
 
For DHCW - At time End-of- Study (Day 28)
 
% Surveys Completed:
 
For DHCW - At time End-of- Study (Day 28)
 

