#### End of Study- Day 28 (+/- 14 days)

- Undergo a three-part COVID-19 triage screening\*
  - Symptom questions
  - o Temperature check
  - Pulse oximeter reading
  - Complete two SARS-CoV-2 tests\*\*
    - SARS-CoV-2 POC test
      - A nasal swab will sweep the inside of the participant's nose to collect your specimen for the SARS-CoV-2 test
      - The office staff will process the specimen
    - ELISA Antibody test
      - A small lancet will create a finger prick to collect a small blood sample
      - The sample will be sent to and processed by the PHRI lab
  - Complete two electronic surveys:
    - DHCW End of Study Survey- Questions include importance of triage and testing, importance of PPE measures, perceptions of safety and comfort in the workplace, safety culture in the office, SARS-CoV-2 testing preferences, dentists role in SARS-CoV-2 testing, willingness to test in the office, and vaccinations
    - DHCW Participation Survey- Questions explore perceptions related to study participation including survey and testing logistics
    - 29 questions in the two surveys put-together

If any aspect of the COVID-19 triage screening is positive, the DHCW will be excused from work and referred to their primary care physician for further testing.

[figure not shown]

Based on NIDCR Observational Protocol Template v4.0-20190909

- Positive screening include having one or more symptoms
- A positive temperature is considered greater than 100.4 degrees F
- A positive pulse oximeter is considered when the blood oxygen saturation level is below 95%

The results of the POC test and the lab processed SARS-CoV-2 antibody test will be recorded in the *Testing Case Report* form in REDCap.

- If **POSITVE**: The Clinic Director or one of the co-investigators will communicate positive results to the participant upon receipt. Positive participants will be dismissed from duties and instructed to consult with their primary care provider for further testing.
- If **NEGATIVE**: The Clinic Director or one of the co-investigators will communicate negative results to the participant.

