#### 11.3 Final Analysis Plan

Data to be collected includes:

	Type of Variable	4
Willingness to Participate	
 
Willingness to participate (Binary – Yes/No)
 
	]
Dentist, Hygienist, Assistant and Front Desk		
personnel willing to participate		4
Triage Survey	Ease of Administration (3 point Likert Scale)	
	
 
Very easy to complete survey due to administration
 
	
	method ◦ Easy to administer complete survey due to	
	
 
administer complete survey due to administration method
 
	
	
 
Not easy to complete survey due to survey
 
	
	administration method	
	Completeness (Binary – Yes/No)	
	Question understandability (3 point Likert Scale)	
	
 
Very clear to understand
 
	
	$\circ~$ Understandable with some clarification provided by	
	the administrator	
	Not clear to understand	4
Safety Perception Survey	Administration method (3 point Likert Scale)	
Start-of-Study DHCW Survey	
 
Very easy to complete survey due to administration
 
	
End-of-Study DHCW Survey	method ○ Easy to complete survey due to administration	
	method	
	
 
Not easy to complete survey due to administration
 
	
	method	
	
 
Completeness (Binary – Yes/No)
 
	
	
 
Question understandability (3 point Likert Scale)
 
	
	
 
Very clear to understand
 
	
	
 
Understandable with some clarification provided by
 
	
	the administrator	
	• Not clear to understand	-
Festing Logistics	
 
Specimen Collection (3 point Likert Scale)
 
Very easy to collect
 
	

 
POC – BD Veritor SARS-CoV-2 antigen test
 
ELISA antibody SARS-CoV-2 test
 
	
 
Easy to collect
 
	
	
 
Not easy to collect
 
	
	• Specimen preparation for shipping (3 point Likert Scale)	
	
 
Very easy to prepare
 
	
	
 
Easy to prepare
 
	
	
 
Not easy to prepare
 
	
	
 
Specimen storage until processing (Binary – Easy/Not
 
	
	Easy)	
	
 
Easy to Store
 
	
		RUTGERS   eI APPROVED
		ADDOVED
ased on NIDCR Observational Protocol Tem	uplate v4 0–20190909	AFFROVED

Based on NIDCR Observational Protocol Template v4.0–20190909

	
 
Not easy to store
 

	
 
Timeliness of results (3 point Likert Scale)
 

	
 
Very timeless access to results
 

	
 
Timely access to results
 

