	
 
Access to results not timely
 

	
 
Reporting of results (3 point Likert Scale)
 

	
 
Very easy to access results
 

	
 
Easy to access results
 

	
 
Not easy to access results
 

Testing Case Report	
 
Completeness (Binary – Yes/No)
 

Descriptive statistics (frequencies) for all variables will be analyzed.

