#### **Subject Completion Review**

As this is a feasibility study, reviews of surveys and case reports to ensure completeness will not be completed, rather the number/percentage of incomplete survey's and forms will be analyzed as an outcome measure. Consent forms will be reviewed for completeness at the mid-study visit for DHCW subjects and as part of the end-of-visit survey for patient subjects.

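### Section 11.1 promises to test three feasibility hypotheses, but section 11.3 supplies only frequencies; promise estimation instead, with exact 95% intervals

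*Combined protocol and SAP*

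**What the plan says.** Section 11.1 states that workers will be willing to participate and that surveys and testing protocols will be easy to complete, and adds "Analyses will be performed to test these hypotheses". Section 11.2 describes a feasibility study to refine logistics and makes no sample size calculation. Section 11.3 lists the variables and their scales, then gives the whole analysis in one sentence: "Descriptive statistics (frequencies) for all variables will be analyzed".

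The supporting definitions are elsewhere:

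- **Size.** The target is 20 (section 5.3). The Protocol Summary makes this an upper limit.
- **Willingness.** Section 3.0 defines it as workers agreeing over all workers asked.
- **Completion.** Section 3.0 lists the percentage completing the study and the percentage completing the Start-of-Study and End-of-Study surveys.
- **Ratings.** Ease and understandability are assessed at Day 28. The participation survey given then is described as "Questions explore perceptions related to study participation including survey and testing logistics".
- **Understandability.** Section 3.0 words it as those "who feel survey questions were understandable" and, in the time-frame column, as those "indicating survey questions were easy to understand". The middle response in 11.3 begins "Understandable with some clarification provided by" and goes on to name the administrator.
- **Form completeness.** Section 13 (Subject Completion Review) says "the number/percentage of incomplete survey's and forms will be analyzed as an outcome measure". Under Data Management Controls, the same section says REDCap requires every response at completion.

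**The concern.** A hypothesis test needs a null value or criterion, an error rate and a decision rule. The plan has none of these, so the sentence in 11.1 commits the study to something 11.3 cannot deliver. The percentages are the pilot's results, and section 4 says they may inform a larger grant application. If they are reported bare under a promise of testing, a high percentage may be read as a hypothesis confirmed, when the sample leaves wide uncertainty about the underlying rate.

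**Working it through.** The plan states no power, error rate or interval, so there is no figure of its own to reproduce. The checks below show what 20 people can support.

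**1. Precision.** Input: n = 20 (section 5.3), or fewer, because 20 is a ceiling. The observed counts are assumptions. For x of n, the Clopper-Pearson 95% limits are the 0.025 quantile of Beta(x, n − x + 1) and the 0.975 quantile of Beta(x + 1, n − x). When x = n, the lower limit reduces to 0.025^(1/n).

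| Result | Percentage | Exact 95% interval |
|---|---|---|
| 20/20 | 100% | 83.2% to 100%, since 0.025^(1/20) = 0.832 |
| 18/20 | 90% | 68.3% to 98.8% |
| 15/20 | 75% | 50.9% to 91.3% |
| 10/20 | 50% | 27.2% to 72.8% |
| 10/10 | 100% | 69.2% to 100%, since 0.025^(1/10) = 0.692 |

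Willingness uses the number asked, which the plan does not give. If 20 agree out of an assumed 25, the result is 80% (59.3% to 93.2%). Out of an assumed 40, it is 50% (33.8% to 66.2%).

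**2. What a test would require.** Assume one-sided alpha 0.05, n = 20 and a true rate of 0.90. The rule is the smallest r with P(X ≥ r | p0) ≤ 0.05.

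| Assumed p0 | Required count | Exact alpha | Power |
|---|---|---|---|
| 0.50 | 15 | 0.021 | 0.989 |
| 0.60 | 17 | 0.016 | 0.867 |
| 0.70 | 18 | 0.035 | 0.677 |
| 0.80 | 20 | 0.012 | 0.122 |
| 0.90 | none | – | – |

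At p0 = 0.90 even 20/20 is not significant, since 0.90^20 = 0.122. The same data could confirm or fail to confirm ease depending on a null value that the plan never states.

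**3. Rating denominator.** Early leavers are not replaced (5.4.2) and have no withdrawal visit (6.2), so raters are in effect completers. With x rating easy among r raters of n enrolled, x/r − x/n ≤ (n − r)/n. At n = 20 the gap is at most 1/20 = 5 points per non-rater, and zero if nobody is lost.

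**4. Understandability.** With 20 raters, each middle-category answer moves the percentage by 1/20 = 5 points, depending on the side to which it is assigned.

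**5. Repeated forms.** Section 7.1 schedules Triage and Testing Case Reports at three visits: 3 × 20 = 60 of each. One person leaving after Day 0 leaves two of each unstarted. Completed over scheduled is then 58/60 = 96.7% for each form type, while completed over started remains 58/58 = 100% if every started form is finished. Because responses are required at completion, the second figure will say little.

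**The case against.** The best defence is that this is a logistics pilot. Descriptive analysis is appropriate, no progression decision hangs on a percentage, and 'test' may have been meant loosely. That stands as a reason for asking for neither power nor a larger sample. It does not rescue the sentence in 11.1, which can be corrected at almost no cost.

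A reader might infer more than the documents support:

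- **That staff-entered and participant-completed forms are pooled.** They are not. Section 11.3 gives completeness separate rows for the Triage Survey, the Start and End surveys, and the Testing Case Report.
- **That survey completion has no person-level measure.** Section 3.0 already has the percentages completing the study and the surveys. The Start and End surveys are each scheduled once per person (6.1), so these are in substance completed over scheduled. Only the repeated Triage and Testing forms lack such a figure.
- **That the rating percentages have no usable denominator.** A percentage of people who feel something ordinarily means those who answered, and study completion is reported alongside.
- **That the understandability result would be lost.** Frequencies for all three categories will be reported, so either cut can be rebuilt. The mention of an administrator also fits the interviewer-completed triage report.

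A further fair point is that an exact interval describes sampling error only. Participants are volunteers invited by investigators in their own department (5.3), so an interval could suggest more generality than exists. The report should say so.

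**Conclusion.** The inconsistency between 11.1 and 11.3 is real: a test is promised, and nothing needed for one is specified. At the planned size, even unanimous success leaves true rates down to 83.2% compatible with the data at n = 20, and down to 69.2% at n = 10; 15/20 leaves an interval about 40 points wide. These figures assume independent participants and illustrative counts. The design and sample size need no change. The rating denominator, the understandability label and the counting of repeated forms are minor clarifications. None would justify a separate point, and they do not show that the pilot's results are undefined.

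**What to change.** **Main change.** In 11.1, replace the promise to test the hypotheses with a statement that the corresponding proportions will be estimated. In 11.3, report each participant-level percentage as n/N with a Clopper-Pearson 95% interval:

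- willing, of all workers asked;
- study completed;
- all surveys completed;
- rated easy, meaning the top two responses (very easy or easy);
- rated understandable.

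State that the intervals reflect sampling error only, in a volunteer sample from one school.

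**Minor clarifications to add at the same time.**

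- Show the number rating beside the number enrolled, with responders as the main denominator.
- Use one name for the understandability outcome and say on which side the middle category falls.
- Report completeness of the Triage and Testing Case Reports as completed over scheduled forms, keeping the separate rows 11.3 already has.

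**Cost.** Analysis-plan wording, a little more tabulation, and results that look less certain than bare percentages. Instruments, visits and sample size are unaffected.

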#### 11.2 Sample Size Considerations

This is a feasibility study to refine trial logistics. No sample size calculations are being performed.

#### 11.3 Final Analysis Plan

Data to be collected includes:

	Type of Variable	4
Willingness to Participate	
 
Willingness to participate (Binary – Yes/No)
 
	]
Dentist, Hygienist, Assistant and Front Desk		
personnel willing to participate		4
Triage Survey	Ease of Administration (3 point Likert Scale)	
	
 
Very easy to complete survey due to administration
 
	
	method ◦ Easy to administer complete survey due to	
	
 
administer complete survey due to administration method
 
	
	
 
Not easy to complete survey due to survey
 
	
	administration method	
	Completeness (Binary – Yes/No)	
	Question understandability (3 point Likert Scale)	
	
 
Very clear to understand
 
	
	$\circ~$ Understandable with some clarification provided by	
	the administrator	
	Not clear to understand	4
Safety Perception Survey	Administration method (3 point Likert Scale)	
Start-of-Study DHCW Survey	
 
Very easy to complete survey due to administration
 
	
End-of-Study DHCW Survey	method ○ Easy to complete survey due to administration	
	method	
	
 
Not easy to complete survey due to administration
 
	
	method	
	
 
Completeness (Binary – Yes/No)
 
	
	
 
Question understandability (3 point Likert Scale)
 
	
	
 
Very clear to understand
 
	
	
 
Understandable with some clarification provided by
 
	
	the administrator	
	• Not clear to understand	-
Festing Logistics	
 
Specimen Collection (3 point Likert Scale)
 
Very easy to collect
 
	

 
POC – BD Veritor SARS-CoV-2 antigen test
 
ELISA antibody SARS-CoV-2 test
 
	
 
Easy to collect
 
	
	
 
Not easy to collect
 
	
	• Specimen preparation for shipping (3 point Likert Scale)	
	
 
Very easy to prepare
 
	
	
 
Easy to prepare
 
	
	
 
Not easy to prepare
 
	
	
 
Specimen storage until processing (Binary – Easy/Not
 
	
	Easy)	
	
 
Easy to Store
 
	
		RUTGERS   eI APPROVED
		ADDOVED
ased on NIDCR Observational Protocol Tem	uplate v4 0–20190909	AFFROVED

Based on NIDCR Observational Protocol Template v4.0–20190909

	
 
Not easy to store
 

	
 
Timeliness of results (3 point Likert Scale)
 

	
 
Very timeless access to results
 

	
 
Timely access to results
 

	
 
Access to results not timely
 

	
 
Reporting of results (3 point Likert Scale)
 

	
 
Very easy to access results
 

	
 
Easy to access results
 

	
 
Not easy to access results
 

Testing Case Report	
 
Completeness (Binary – Yes/No)
 

Descriptive statistics (frequencies) for all variables will be analyzed.

## 12 SOURCE DOCUMENTS AND ACCESS TO SOURCE DATA/DOCUMENTS

All study survey information will be captured electronically and stored on secure, encrypted Rutgers University servers.

- Consents will be captured and recorded directly into the REDCap system.
- All DHCW surveys will be recorded directly into REDCap via the following REDCap forms:

DHCW Participants
Start-of-Study DHCW Survey
Triage Survey Case Report
End-of-Study DHCW Survey
DHCW Participation Questionnaire
Testing Case Report

• Testing results will be captured in the REDCap Testing Case Report in the following ways:

	POC	ELISA
Original Source	N/A – Results appear on	Excel Spreadsheet
Document	BD Veritor Screen and	posted onto SDM
	directly recorded into	PREDICT box drive
	REDCap	
Storage of Original	Not Applicable	Electronically stored on
Source Document		Rutgers server
Responsibility for	Research Clinical	Research Clinical
Entering into REDCap	Director	Director or Research
	Or Research Assistant	Assistant
Verification of Correct	Not Applicable	PI or Chief of Clinical
Entry into REDCap		Protocol

All paper based study source documents will be maintained in the Rutgers School of Dental Medicine Clinical Research Center which is located on the D Level of the Dental School Building. All documents will be secured in a locked file cabinet in the center. Access to the Clinical Research Center is limited to research center personnel via a card reader.

Study staff will maintain appropriate medical and research records for this study, in compliance with ICH E6, Section 4.9 and regulatory and institutional requirements for the protection of confidentiality of participants. Study staff will permit authorized representatives of NIDCR and regulatory agencies to examine (and when required by applicable law, to copy) research records for the purposes of quality assurance reviews, audits, and evaluation of the study safety, progress, and data validity.

## **13 QUALITY CONTROL AND QUALITY ASSURANCE**

Quality Management (QM) measures will occur throughout this study to ensure adherence to protocol and collection of high quality data. QM activities include those measures done as part of daily standard operating procedures by staff at each site and by the data management controls built into the PREDICT REDCap to ensure adherence to the protocol and collection of complete and accurate data. QM activities will include activities undertaken at defined intervals to check that QM activities are taking place and study-related documents are up-to-date.

#### Staff Training

Training of all staff will be conducted and recorded in training logs. Each staff member has been identified by role. Records of completed training will be maintained in each study member's study personnel file kept on the SDM PREDICT box drive, Personnel Qualifications folder.

Training Modules	Who Will be Trained
Human Subjects, HIPAA	All Study Personnel
General Clinical Research Training (Human Subjects, HIPAA)	PI, Chief of Clinical Protocol
General Overall (Study Purpose, Goals and Protocol)	All Study Personnel
REDCap System Training	Research Clinical Directors and Research Assistants

#### **Daily Operating Procedures**

Quality management measures have been built into Clinical Protocol Core and site procedures.

#### **Subject Completion Review**

As this is a feasibility study, reviews of surveys and case reports to ensure completeness will not be completed, rather the number/percentage of incomplete survey's and forms will be analyzed as an outcome measure. Consent forms will be reviewed for completeness at the mid-study visit for DHCW subjects and as part of the end-of-visit survey for patient subjects.

#### **Data Management Controls**

REDCap is a rich system which enables privileging, required data element entry and required data validation to be embedded into daily operations.

- **Privileging:** Every study staff member will be assigned a role which carries specific read/write/edit/delete privileges. Staff member will be assigned a role providing minimal rights sufficient to perform his/her responsibilities.
- **Structured Data:** Whenever possible, data will be collected via structured data responses rather than free-text. Structured data requires a respondent to check a valid response.
- **Data Validation:** Data fields will be established limiting responses to those that are reasonable. For example, year of birth would have a range of 2002 (corresponding to age 18 – the youngest eligible) to 1920 (corresponding to age 100 – more than sufficient to cover the age range of individuals having impacted 3rd molars extracted.)
- **Required Fields:** Whenever appropriate, fields have been made required so as to ensure completed forms and questionnaires.

Structured responses are required for the CRFs so only valid responses can be recorded. In addition, REDCap has been programmed with all responses being required at time of completion. Validation rules are employed where possible.

## 14 ETHICS/PROTECTION OF HUMAN SUBJECTS

#### 14.1 Ethical Standard

The investigator will ensure that this study is conducted in full conformity with the principles set forth in The Belmont Report: Ethical Principles and Guidelines for the Protection of Human Subjects of Research, as drafted by the US National Commission for the Protection of Human Subjects of Biomedical and Behavioral Research (April 18, 1979) and codified in 45 CFR Part 46 and/or the ICH E6.

